6.4 Baseline

Refer to [Section 10.4](#) for baseline definitions of vital signs, weight and laboratory assessments, unless noted otherwise for a particular assessment.

Physical examination, ECOG performance status, hematology or serum chemistry does not need to be performed if the screening examination was performed within 7 days of the first dose of IP in the treatment phase. Assessment of bleeding events, and the FACT-An and EQ-5D questionnaires start on Day 1 of Cycle 1. The FACT-An and EQ-5D questionnaires should always be completed prior to IP administration and, when feasible, prior to interaction with study personnel.

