10.4 Background and Demographic Characteristics

Demographic and baseline disease characteristics will be summarized by treatment group for the ITT, mITT, and safety populations. Subjects' age, height, weight, body mass index (BMI), and continuous baseline characteristics will be summarized using descriptive statistics (N, mean, SDev, median, minimum, maximum), while age group, gender, race and other categorical variables will be provided using frequency tabulations (count, percent) by treatment group. Summaries of baseline disease characteristics will include WHO MDS diagnosis classification, IPSS risk classification, time since initial MDS diagnosis, ECOG performance status, bone marrow blasts (%), Hgb (g/dL), platelet counts ($10^9/L$), average baseline RBC transfusion requirement

(unit of RBC per 28 days), platelet transfusion status (dependent or independent), and IPSS cytogenetic classification. For laboratory and vital sign measures, the most recent assessment on or prior to the date of randomization will be used for baseline. Baseline transfusion history will include all transfusions up to and including the date of randomization.

Medical history data (coded by the Medical Dictionary for Regulatory Affairs [MedDRA] dictionary) will be summarized using frequency tabulations by treatment group, system organ class and preferred term for the ITT, mITT, and safety populations.

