^a Pre-treatment counts averages of at least 2 measurements (not influenced by transfusions, ie, no RBC transfusions for 2 weeks and no platelet transfusions for 1 week) ≥ 1 week apart (modification).

[figure not shown]
^b Modification to IWG (2000) response criteria.

^c In the absence of another explanation, such as acute infection, repeated courses of chemotherapy (modification), gastrointestinal bleeding, hemolysis, and so forth. It is recommended that the 2 kinds of erythroid and platelet responses be reported overall as well as by the individual response pattern.

[figure not shown]
Note: Deletions to the IWG response criteria are not shown. To convert hemoglobin levels from grams per deciliter to grams per liter, multiply grams per deciliter by 10.

Source: Cheson BD, Greenberg PL, Bennett JM, Lowenberg B, Wijermans PW, Nimer SD et al. Clinical application and proposal for modification of the International Working Group (IWG) response criteria in myelodysplasia. *Blood* 2006; 108 (2): 419-25.

[figure not shown]

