8. DEMOGRAPHICS AND BASELINE CHARACTERISTICS

Summaries for the demographics and baseline clinical characteristics will be summarized by treatment group for ITT, mITT and the Safety population. Baseline clinical characteristics are defined as the latest data collected on or before date of randomization, if not otherwise specified. When there are retested values, the retest values will be used for the analysis. Individual subject listings will be provided to support the tables.

Summary statistics (mean, standard deviation, median, minimum, and maximum) will be provided for variables measured on a continuous scale. The frequency distribution (n, %) will be provided for those categorical variables measured on a nominal scale.

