8.2. Baseline Disease Characteristics

Baseline disease characteristics includes following variables:

- MDS World Health Organization (WHO) 2008 classification,
- Eastern Cooperative Oncology Group (ECOG) performance status (0 – 1, 2),
- Time since initial diagnosis (defined as the number of months from the date of initial diagnosis to the date of randomization),
- IPSS score classification ([Greenberg, 1997, Appendix C](#)),
- Baseline platelet transfusion status (Dependent, Independent),
- Average baseline RBC transfusion requirements (units per 28 days) and category (≤ 4 units per 28 days, > 4 units per 28 days),
- Bone marrow blasts baseline values and category ($< 5\%$, $\geq 5\%$),
- Hgb (g/dL) values,
- Platelet count ($10^9/L$) values,
- Absolute neutrophil count ($10^9/L$) values,
- White blood cell count ($10^9/L$) values,

- Transferrin saturation baseline values (%) values.

Subjects will be considered platelet transfusion dependent at baseline if they have received ≥ 2 platelet transfusions during the 56 days immediately preceding randomization and had no consecutive 28-day period during which no platelet transfusions were administered.

The average number of units (in 28 days) of baseline RBC transfusions is determined by the following rules:

If the subject was randomized under the original protocol and protocol amendment 1, the average number of units per 28 days = sum of RBC transfusion units during the 84-day interval prior to the randomization date / 84 days * 28 days.

- If the subject was randomized under protocol amendment 2, the average number of units per 28 days = sum of RBC transfusion units during the 56-day interval prior to the randomization date / 56 days * 28 days.
- RBC transfusion and whole blood transfusion during the above specified period will be included. For whole blood transfusion, the number of units collected in the CRF will be used to calculate the RBC transfusions required units.

To eliminate the impact of transfusion, the baseline values for Hgb will be determined by following steps:

Step 1: Apply the “7-day rule” on all Hgb values from the Central lab which are collected on or prior to Cycle 1 Day 1. Use the lowest value among the Hgb values which are collected after >7 days of a RBC/whole blood transfusion or collected on the same of the transfusion as the baseline value.

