Step 2: For subjects who don’t have baseline value from Step 1, apply the “7/3-day rule”. Use the lowest value among the Hgb values from the Central lab which are collected within 7 days after a RBC/whole blood transfusion and within 3 days before another transfusion as the baseline value. The rationale is that the Hgb value within 7 days from the first transfusion was only somewhat influenced by that transfusion.

Step 3: For subjects who don’t have baseline values from Steps 1 and 2, use the lowest value among all Hgb values from the Central lab which are collected on or prior to Cycle 1 Day 1.

The baseline values for platelet count will be determined similarly to eliminate the impact of platelet transfusion.

For absolute neutrophil count, white blood cell count and bone marrow blasts, the baseline values will be determined by selecting the last non-missing value from the Central lab on or prior to Cycle 1 Day 1. In case that a randomized subject was not treated (no Cycle 1 Day 1 date), the date of randomization will be used.

Baseline transferrin saturation will be derived using the serum samples collected at screening. The transferrin saturation result is derived as: iron (umol/L) / total iron binding capacity (umol/L). In case the result of total iron binding capacity is reported as “<xxx”, xxx-1 will be used as the total iron binding capacity to derive the transferrin saturation.

By-subject listings of the baseline disease characteristics will be provided.

In addition to the above baseline disease characteristics, the revised international prognostic scoring system for MDS (IPSS-R, [Greenberg, 2012, Appendix G](#)) will be summarized for exploratory purpose.

IPSS-R score will be classified and summarized as: very low, low, intermediate, high, very high. The derivation for the IPSS-R score is provided in [Appendix G](#). The revised IPSS cytogenetic classification (from central lab) will also be summarized (very good, good, intermediate, poor, very poor).

[REDACTED]

By-subject listings of IPSS-R will be provided.

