^d In some circumstances, protocol therapy may require the initiation of further treatment (eg, consolidation, maintenance) before the 4-week period. Such subjects can be included in the response category into which they fit at the time the therapy is started. Transient cytopenias during repeated chemotherapy courses should not be considered as interrupting durability of response, as long as they recover to the improved counts of the previous course.

Notes: Subjects with CMML will be assessed for response using the IWG criteria for MDS. Deletions to IWG response criteria are not shown. To convert hemoglobin from grams per deciliter to grams per liter, multiply grams per deciliter by 10.

Source: Cheson BD, Greenberg PL, Bennett JM, Lowenberg B, Wijermans PW, Nimer SD et al. Clinical application and proposal for modification of the International Working Group (IWG) response criteria in myelodysplasia. Blood 2006; 108 (2): 419-25.

Modified Hematologic Improvement According to IWG Criteria	
Hematologic improvement^a	Response criteria (responses must last at least 8 week)^b
Erythroid Response (HI-E) (pretreatment, <11 g/dL)	Hemoglobin increase by ≥ 1.5 g/dL Relevant reduction of units of RBC transfusions by an absolute number of at least 4 RBC transfusions/8 weeks compared with the pretreatment transfusion number in the previous 8 weeks. Only RBC transfusions given for a hemoglobin of ≤ 9.0 g/dL pretreatment will count in the RBC transfusion response evaluation ^b
Platelet Response (HI-P) (pretreatment, <100 X 10 ⁹ /L)	Absolute increase of ≥ 30 X 10 ⁹ /L for subjects starting with > 20 X 10 ⁹ /L platelets Increase from < 20 X 10 ⁹ /L to > 20 X 10 ⁹ /L and by at least 100% ^b
Neutrophil Response (HI-N) (pretreatment, <1.0 X 10 ⁹ /L)	At least 100% increase and an absolute increase > 0.5 X 10 ⁹ /L ^b
Progression or Relapse After HI ^c	At least 1 of the following: At least 50% decrement from maximum response levels in granulocytes or platelets Reduction in hemoglobin by ≥ 1.5 g/dL Transfusion dependence

KEY: HI = hematologic improvement; HI-E = hematologic improvement erythroid response; HI-N = hematologic improvement neutrophil response; HI-P = hematologic improvement platelet response; IWG = International Working Group; MDS = myelodysplastic syndromes; RBC = red blood cell

a Pretreatment counts averages of at least 2 measurements (not influenced by transfusions) ≥ 1 week apart (modification).

b Modification to IWG response criteria.

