c In the absence of another explanation, such as acute infection, repeated courses of chemotherapy (modification), gastrointestinal bleeding, hemolysis, and so forth. It is recommended that the 2 kinds of erythroid and platelet responses be reported overall as well as by the individual response pattern.

Note: Deletions to the IWG response criteria are not shown. To convert hemoglobin levels from grams per deciliter to grams per liter, multiply grams per deciliter by 10.

Source: Cheson BD, Greenberg PL, Bennett JM, Lowenberg B, Wijermans PW, Nimer SD et al. Clinical application and proposal for modification of the International Working Group (IWG) response criteria in myelodysplasia. Blood 2006; 108 (2): 419-25.

18.6. Appendix F: Derivation Rules for Hematologic Response and Hematologic Improvement According to the IWG Criteria for MDS

Following rules will be used to derive the hematologic response, cytogenetic response, and hematologic improvement using central lab data, including [redacted] central lab data for bone marrow. Lab data collected after the date of the end of treatment visit, or last dose date + 28 days, whichever occurs later, will not be used.

In the following derivations, if Hgb or platelet counts are used for evaluation, the Hgb values are only valid to use if there is no RBC/Whole blood transfusion within 7 days prior to the sample collection, the platelet count values are only valid to use if there is no platelet transfusion within 7 days prior to the sample collection.

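### SAP 18.6.3 contradicts itself on which RBC transfusions count toward HI-E, and names no starting value for the central-lab platelet and hemoglobin responses

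*SAP*

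**What the plan says.** **HI-E transfusion limb.** A response needs at least 4 fewer RBC units over 8 weeks than before treatment. Four places say which transfusions count:

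- Protocol Appendix D: those given at Hgb ≤ 9.0 g/dL on treatment.
- SAP Appendix E: those given at Hgb ≤ 9.0 g/dL pretreatment.
- SAP 18.6.3 (Appendix F): those given at Hgb ≤ 10.0 g/dL on treatment.
- SAP 10.2.11, which 18.6.3 uses to confirm the response: all units in both 56-day windows, with no Hgb cut-off.

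**Starting value.** SAP 18.6.3 asks for a platelet rise of at least 30 × 10⁹/L from above 20, or at least a doubling from 20 or below to above 20. The Hgb limb of HI-E asks for a rise of at least 1.5 g/dL. Neither names the value from which the rise is measured. The same section does name baseline ANC for HI-N and baseline 56-day units for the transfusion limb.

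Two rules in the SAP could fill the gap:

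- SAP 8.2, Step 1, for Hgb: "Use the lowest value among the Hgb values which are collected after >7 days of a RBC/whole blood transfusion". It adds: "The baseline values for platelet count will be determined similarly to eliminate the impact of platelet transfusion".
- SAP Appendix E, footnote a to the hematologic-improvement table: "Pretreatment counts averages of at least 2 measurements (not influenced by transfusions"), taken at least a week apart. Protocol Appendix D has the same footnote and defines freedom from transfusion as "no RBC transfusions for 2 weeks and no platelet transfusions for 1 week".

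The Appendix F introduction limits which values may be used ("the Hgb values are only valid to use if there is no RBC/Whole blood transfusion within 7 days prior to the sample collection", and likewise for platelets), but not how one is chosen. SAP 16 lists neither matter among its changes to the protocol.

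**The concern.** HI-P and HI-E are named secondary endpoints, and SAP 10.2.2 compares HI-P between arms with the primary-endpoint method. Two competent programmers could follow this text and report different rates from the same data, and a reader could not tell which definition lay behind a rate.

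The transfusion limb is more than an omission. A filter applied to on-treatment units but not to baseline units counts the two windows on different scales, so a subject whose transfusion burden has not changed can be recorded as improved.

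**Working it through.** The plan states no figure for these endpoints, so there is none to reproduce. What follows is arithmetic on the written rules, with illustrative subjects.

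**1. Transfusion limb.** Reduction = counted units before − counted units on treatment; response if ≥ 4. Both subjects receive 8 units in the 56 days before randomization and 8 in a 56-day window on treatment, so nothing has changed.

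- Subject A: 4 of each 8 given above Hgb 10.0, the other 4 at ≤ 9.0. The 4 qualifying units are 4 / 56 × 28 = 2 per 28 days, so this subject can meet the entry requirement.
- Subject B: 4 of each 8 given at Hgb 9.1–10.0, the other 4 at ≤ 9.0.

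| Rule read literally | A: before − on = reduction | B: before − on = reduction |
|---|---|---|
| SAP 18.6.3 filter (≤ 10.0, on treatment) | 8 − 4 = 4, responder | 8 − 8 = 0 |
| SAP 10.2.11 (no cut-off) | 8 − 8 = 0 | 8 − 8 = 0 |
| Protocol Appendix D (≤ 9.0, on treatment) | 8 − 4 = 4, responder | 8 − 4 = 4, responder |
| SAP Appendix E (≤ 9.0, pretreatment) | 4 − 8 = −4 | 4 − 8 = −4 |

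**2. How the two parts of 18.6.3 interact.** Let B be baseline units, T on-treatment units and T₁₀ those of T given at Hgb ≤ 10.0. The filter gives B − T₁₀ and 10.2.11 gives B − T. As T₁₀ ≤ T, the filtered reduction is never the smaller one. If both must reach 4, section 10.2.11 alone decides and the ≤ 10.0 sentence does nothing. If the ≤ 10.0 sentence decides, Subject A is a false responder. No reading makes the sentence both effective and fair to the two windows.

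**3. Starting value.** The target follows from the 18.6.3 criteria: twice the start (and above 20) if the start is ≤ 20, start + 30 if above 20, and start + 1.5 for Hgb.

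| Eligible values | Lowest (SAP 8.2) → target | Average (Appendix E, footnote a) → target |
|---|---|---|
| Platelets 30, 48 | 30 → 60 | 39 → 69 |
| Platelets 19, 29 | 19 → 38 | 24 → 54 |
| Hgb 7.6, 8.8 | 7.6 → 9.1 | 8.2 → 9.7 |

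A platelet count held at 65 in the first row is a response under one rule and not under the other. For the same eligible values the lowest-value target is never above the average-value target, so the lowest-value rule can only leave a rate the same or raise it.

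**4. Section 8.2 does not fit Appendix F.** Steps 2 and 3 of 8.2 accept Hgb values taken within 7 days after a transfusion. Appendix F and 18.6.3 bar those values.

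**The case against.** **Section 8.2 may be the SAP-wide default.** The SAP restates a baseline where it wants a different one: the laboratory baseline in 11.3, and the worst Hgb and platelet values for IPSS-R in Appendix G. Silence in 18.6.3 might therefore mean 8.2. That is plausible but not settled. Section 18.6.3 does not cite 8.2, Steps 2 and 3 clash with it, and SAP 10.2.2 and 10.2.10 define the endpoints by Appendix E, whose footnote says average. If 8.2 was meant, it departs from that definition and SAP 16 should say so.

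**Appendix F is the operative derivation; Appendix E only reproduces the criteria.** This largely stands. Within the SAP the working conflict on transfusions is then ≤ 10.0 on treatment against no cut-off, and the two differ only when some on-treatment transfusions are given above Hgb 10.0. Subject B's result under Protocol Appendix D needs that table to be applied literally.

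**A reader might infer a third starting value, the most recent one.** Protocol 10.4 says "For laboratory and vital sign measures, the most recent assessment on or prior to the date of randomization will be used for baseline". But Protocol 6.4 points there for "baseline definitions of vital signs, weight and laboratory assessments, unless noted otherwise for a particular assessment", and the SAP 8 default reads "Baseline clinical characteristics are defined as the latest data collected on or before date of randomization, if not otherwise specified". Both yield to the specific rules above, so the live choice is lowest against average.

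**A reader might also infer a bias between arms or an inflated type I error.** The documents do not support this. The same rules apply to both blinded arms, and nothing in the plan makes them favor one.

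**Conclusion.** The point holds. On the HI-E transfusion limb, SAP 18.6.3 gives two incompatible counts, and both IWG tables differ from it and from each other; this rests on the text alone. On the starting value, the gap is real and the choice is between the lowest value and an average of at least two.

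The effect on reported rates cannot be computed. The documents give no within-subject variability, no count of eligible screening values and no distribution of Hgb at transfusion. The examples show that individual classifications can change, not how often.

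The consequence is limited. HI-P and HI-E lie outside the alpha-controlled sequence (SAP 10.2). The primary endpoint, OS and the separately summarized CRF-collected HI responses do not use these derivations.

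**What to change.** **Transfusion limb.** Reconcile Protocol Appendix D, SAP Appendix E, SAP 18.6.3 and SAP 10.2.11 to one counting rule applied identically to the baseline and on-treatment 56-day windows, and remove the one-window cut-off from 18.6.3. One workable choice is the 10.2.11 count with no cut-off in either window, with ≤ 9.0 in both windows as a labelled sensitivity analysis. Neither table states ≤ 9.0 for both windows, and under it subjects who qualified on transfusions at 9.1–10.0 may have fewer than 4 counted baseline units and be unable to respond on that limb. This is a rule for counting an endpoint, not for when to transfuse.

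**Starting value.** State it in 18.6.3: the footnote-a average where at least 2 values are valid under the 7-day rule of Appendix F; otherwise the single valid value; otherwise not evaluable on that limb. Report the number in each group by arm. Give the 8.2 lowest-value version as a sensitivity analysis.

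The 7-day rule is the practical one for Hgb. Assume regular transfusions every 28, 21 or 14 days and two samples 14 days apart. With Protocol Appendix D's 2-week window both samples are never valid: if the first is 14 or more days after a transfusion, another transfusion falls before the second. With the 7-day window both are valid for 14/28 = 50%, 7/21 = 33% and 7/14 = 50% of timings.

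**Declaration.** List both choices in SAP 16. The SAP was signed in March 2019 and the Amendment 6.0 rationale says the primary clinical study report is final, so state which rules were used and label any re-analysis post hoc.

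**Cost.** Minor reprogramming. HI rates may be slightly lower than under the lowest-value start or the one-window filter, and some subjects will not be evaluable on the Hgb limb.

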8.3. Medical History

A summary of medical and surgical history will be presented by treatment group and system organ class (SOC) Medical Dictionary for Regulatory Activities (MedDRA) version 21.0 or higher. A by-subject listing of medical and surgical history will also be presented.

8.4. Prior MDS Treatment

A frequency table by Anatomical Therapeutic Chemical (ATC) coding scheme of the World Health Organization (WHO) (March 2018 version, or higher) and preferred name will be provided. A by-subject listing of all prior MDS treatments given will also be presented.

8.5. Prior Cancer, Systemic Anti-cancer Therapy (Not for MDS) and Prior Radiation Therapy

A frequency tabulation of the number of subjects with prior cancer and prior systemic anti-cancer therapy will be provided. A listing of types of prior cancer and all prior systemic anti-cancer therapies documented on the CRF will also be presented.

A frequency tabulation of the number of subjects with prior radiation therapy, the types of radiation therapy used as well as descriptive statistics on the dose received will be given. A listing of all prior radiation therapies documented on the CRF will also be presented.

8.6. Prior Thrombocytopenia Therapy

A frequency tabulation of the number of subjects with prior thrombocytopenia therapy and the types of therapy given. A listing of all prior thrombocytopenia therapies as well as the date the thrombocytopenia was first reported as documented on the CRF will also be presented.

8.7. Prior Medications

Prior medications are defined as medications that were started before the date of first dose (whether or not ended before the date of first dose). Prior medications that continue into study treatment period will be also reported as concomitant medication.

Prior medications will be coded using WHO March 2018 version, or higher. Medication not in the WHO drug dictionary will be classified as “Not Coded” in the analysis.

A frequency table by ATC class and preferred name will be provided. A listing of prior medications documented on the CRF will also be provided.

8.8. Coombs Test Results

A by-subject listing of baseline Coombs test results and reticulocyte count based on the data collected on the CRF page will be provided.

8.9. Subsequent MDS Therapies

Subsequent MDS therapies will be summarized by ATC level 1 term and preferred name for the safety population, respectively. Details of subsequent MDS therapies will be presented in subject data listings.

